5.1.2. Decision rules

The interim and the primary analyses for each endpoint will be performed based on the Full Analysis Set after all patients have been randomized in the study and the target number of events has occurred as described below. A maximum of 4 distinct analyses cutoffs are planned in the study:

- at the time when approximately 235 PFS events (70% of the expected 336 events) by BICR assessment have occurred in PD-L1 positive patients, and all patients have been randomized in the study (IA for PFS and IA1 for OS);
- at the time when 336 PFS events by BICR assessment have occurred in PD-L1 positive patients, and the last patient randomized in the study has been followed for at least 12 months after randomization (primary analysis for PFS and IA2 for OS);
- 15 months after the primary analysis for PFS (IA3 for OS);

- at the time when 368 deaths have occurred in PD-L1 positive patients (primary analysis for OS).

A maximum of two analyses will be performed for PFS (in PD-L1 positive patients and in patients unselected for PD-L1 expression):

1. an interim analysis after all patients have been randomized in the study and at least 235 (70%) of the 336 PFS events in PD-L1 positive patients have been documented by BICR, and
2. the final analysis for PFS after all patients randomized in the study have been followed for 12 months and at least 336 PFS events in PD-L1 positive patients have been documented by BICR.

A maximum of four analyses will be performed for OS (in PD-L1 positive patients and in patients unselected for PD-L1 expression):

1. an interim analysis at the time of the interim analysis for PFS;
2. an interim analysis at the projected time of the final analysis for PFS;
3. an interim analysis 15 months after the final analysis for PFS;
4. a final analysis for OS when 368 deaths in PD-L1 positive patients are observed.

To protect the integrity of the study and to preserve the type I error rate, a gatekeeping testing strategy is implemented and the significance levels for the interim and final efficacy analyses for each endpoint will be determined by using the Lan-DeMets procedure with an O'Brien-Fleming stopping boundary as described in Section 5.1.1.

Table 5 displays the maximum number of analyses expected for each of the primary endpoints and the associated efficacy and futility boundaries if the analyses are performed at the planned number of events as shown in the table. The futility boundaries are non-binding but the study may be stopped for futility if at the time of the first interim analysis, both PFS and OS in PD-L1 positive patients cross the corresponding futility boundaries. If the efficacy boundary is crossed, for either of the primary endpoints, at the time of an interim analysis or at the time of the primary analysis then the primary objective of the study will have been demonstrated.

Table 5. PFS and OS in PD-L1 positive patients – Efficacy and Futility Boundaries

Endpoint	PFS in PD-L1 positive patients		OS in PD-L1 positive patients			
	IA1	PA	IA1	IA2	IA3	PA
Analysis cutoff trigger	235 PFS events in PD-L1+	336 PFS events in PD-L1+	235 PFS events in PD-L1+	336 PFS events in PD-L1+	15 months after IA2	368 deaths in PD-L1+
Number of events (Information fraction)	235 (70%)	336 (100%)	125 (34%)	195 (53%)	294 (80%)	368 (100%)
p-value (z-value) for efficacy	<0.0006 (<-3.2493)	<0.0038 (<-2.6682)	<0.00007 (<-3.7913)	<0.0015 (<-2.9686)	<0.0093 (<-2.3524)	<0.0180 (<-2.0975)
p-value (z-value) for futility ^a	>0.4059 (>-0.2380)	NA	>0.6411 (>0.3614)	>0.3672 (>-0.3394)	>0.0879 (>-1.3537)	NA

^a Non-binding.
 IA1 = interim analysis 1, IA2 = interim analysis 2, IA3 = interim analysis 3, PA = primary analysis
 The observed number of events at the IAs may not match the planned number of events. The efficacy and futility boundaries will be updated based on the actual number of observed events using the pre-specified α - and β -spending functions.

Table 6 displays the analyses triggers for PFS and OS in patients unselected for PD-L1 expression, as well as the associated efficacy boundaries if the analyses are performed at the planned number of events as shown in the table. As described in Section 5.1.1, the significance level for the analyses of these endpoints is determined by the gatekeeping procedure.

Table 6. PFS and OS for patients unselected for PD-L1 expression – Efficacy Boundaries

Endpoint	PFS in patients unselected for PD-L1 expression		OS in patients unselected for PD-L1 expression			
	IA1	PA	IA1	IA2	IA3	PA
Analysis cutoff trigger	235 PFS events in PD-L1+	336 PFS events in PD-L1+	235 PFS events in PD-L1+	336 PFS events in PD-L1+	15 months after IA2	368 deaths in PD-L1+
Number of events ^a (Information fraction)	343 (70%)	490 (100%)	182 (34%)	283 (53%)	427 (80%)	534 (100%)

Endpoint	PFS in patients unselected for PD-L1 expression		OS in patients unselected for PD-L1 expression			
	IA1	PA	IA1	IA2	IA3	PA
Analysis cutoff trigger	235 PFS events in PD-L1+	336 PFS events in PD-L1+	235 PFS events in PD-L1+	336 PFS events in PD-L1+	15 months after IA2	368 deaths in PD-L1+
fraction)						
p-value (z-value) for efficacy ^b	<0.0006 (<-3.2478)	<0.0038 (<-2.6683)	<0.00012 (<-3.6656)	<0.0020 (<-2.8726)	<0.0115 (<-2.2727)	<0.0212 (<-2.0286)
^a Number of events expected under H ₁₃ for PFS (assuming a HR of 0.7) and H ₁₄ for OS (assuming a HR of 0.75). ^b The p-values and z-values noted for OS are those associated with the scenario when both H ₀₂ and H ₀₃ are rejected. IA1 = interim analysis 1, IA2 = interim analysis 2, IA3 = interim analysis 3, PA = primary analysis The observed number of events at the IAs may not match the planned number of events. The efficacy and futility boundaries will be updated based on the actual number of observed events using the pre-specified α -spending functions.						

Since the observed number of events at the interim analysis may not be exactly equal to the planned number of events, the efficacy and futility boundaries will be updated based on the actual number of observed events using the pre-specified α - and β -spending functions. Therefore, the observed Z-test statistic at the interim analysis will be compared with the updated efficacy and, for the primary endpoints, futility boundaries. If the study continues to final analysis, the p-value that will be used to declare statistical significance at the final analysis for each endpoint will be based on the actual number of events documented at the cut-off date for the final analysis, the α already spent at the interim analysis and the gatekeeping testing strategy. Further details are provided in Section 7.

Based on the stopping boundaries defined above and the timing of the interim and final analyses as described above, the design has the following operating characteristics.

Table 7 Simulated cumulative probabilities to stop for efficacy or futility at the interim or final PFS analysis in PD-L1 positive patients

Scenario	Look	Number of PFS events	Calendar Time (months)	P(Reject H ₀₁)	P(Reject H ₁₁)
H ₀₁ is true (HR=1)	Interim	235	23	0.0008	0.5933
	Final	336	29	0.0049	0.9951
H ₁₁ is true (HR=0.65)	Interim	235	25	0.5088	0.0011
	Final	336	32	0.8918	0.1082

Simulations performed in EAST 6.3 with number of simulations = 10,000 and seed=1441014

Table 8. Simulated cumulative probabilities to stop for efficacy or futility at the interim or final OS analyses in PD-L1 positive patients

Scenario	Look	Number of OS events	Calendar Time (months)	P(Reject H_{02})	P(Reject H_{12})
H_{02} is true (HR=1)	Interim 1	125	23	0.0001	0.3668
	Interim 2	195	29	0.0013	0.6554
	Interim 3	294	41	0.0100	0.9156
	Final	368	53	0.0198	0.9802
H_{12} is true (HR=0.70)	Interim	125	25	0.0350	0.0098
	Interim 2	195	32	0.3095	0.0226
	Interim 3	294	46	0.7495	0.0538
	Final	368	61	0.8943	0.1057

Simulations performed in EAST 6.3 with number of simulations = 10,000 and seed=2564105

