5.1.1. Hypotheses and sample size determination

The following statistical hypotheses will be tested to address the primary objectives:

$$H_{01}: HR_{PFS+} \geq 1 \text{ vs } H_{11}: HR_{PFS+} < 1$$

$$H_{02}: HR_{OS+} \geq 1 \text{ vs } H_{12}: HR_{OS+} < 1$$

where HR_{PFS+} and HR_{OS+} are the hazard ratios (Arm A vs. Arm B) of PFS and OS, respectively, in PD-L1 positive patients.

In addition the following statistical hypotheses will be tested to address the secondary objectives:

[figure not shown]
$$H_{03}: HR_{PFS} \geq 1 \text{ vs } H_{13}: HR_{PFS} < 1$$

$$H_{04}: HR_{OS} \geq 1 \text{ vs } H_{14}: HR_{OS} < 1$$

where HR_{PFS} and HR_{OS} are the hazard ratios (Arm A vs. Arm B) of PFS and OS, respectively, for patients unselected for PD-L1 expression.

Overall type I-error will be maintained at or below 1-sided 0.025 by allocating $\alpha=0.004$ (α_1) to the PFS comparison in PD-L1+ patients and by allocating $\alpha=0.021$ (α_2) to the OS comparison in PD-L1 positive patients. A gatekeeping procedure will be used to allow further testing of PFS and OS for patients unselected for PD-L1 expression as described in Figure 1. The significance levels for each test will also take into account the group sequential nature of the design.

Figure 1 Testing Strategy

Approximately 830 patients, including a minimum of 580 PD-L1 positive patients, will be randomized to the treatment arms using a 1:1 randomization, stratified by ECOG PS (0 vs 1) and region (United States vs Canada/Western Europe vs the rest of the world).

For the primary PFS comparison, 336 PFS events by BICR assessment for PD-L1 positive patients will be required to have at least 90% power to detect a hazard ratio of 0.65 using a 1-sided log-rank test at a significance level of 0.004, and a 2-look group sequential design with Lan-DeMets (O'Brien-Fleming) α -spending function to determine the efficacy boundary and a Gamma Family (-15) β -spending function to determine the non-binding futility boundary.

For the primary OS comparison, 368 OS events for PD-L1 positive patients will be required to have at least 90% power to detect a hazard ratio of 0.70 using a 1-sided log-rank test at a significance level of 0.021, and a 4-look group-sequential design with Lan-DeMets (O'Brien-Fleming) α -spending function to determine the efficacy boundary and a Gamma Family (-3) β -spending function to determine the non-binding futility boundary.

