The sample size for this study is determined based on the following:

1. the median PFS for patients receiving sunitinib is 11 months (Sutent Summary of Product Characteristics) and the median PFS for patients receiving avelumab in combination with axitinib is 16.9 months for PD-L1 positive patients and 15.7 months for patients unselected for PD-L1 expression; this, corresponds to a hazard ratio (HR) of 0.65 and 0.7, respectively under the exponential model assumption;
2. the median OS for patients receiving sunitinib is 26.4 months (Sutent Summary of Product Characteristics) and the median OS for patients receiving avelumab in combination with axitinib is 37.7 months for PDL1 positive patients and 35.2 months for patients unselected for PD-L1 expression; this corresponds to a HR of 0.7 and 0.75, respectively under the exponential model assumption;

3. PFS drop-out rate of approximately 15% and OS drop-out rate of approximately 5%;
4. 70% of the randomized patients are PD-L1 positive;
5. non-uniform patient accrual accomplished over a 21 month period.

The sample size of approximately 830 patients will also allow an assessment of PFS and OS in patients unselected for PD-L1 expression.

If H_{01} is rejected then PFS in patients unselected for PD-L1 expression can be tested and 490 PFS events by BICR assessment will be required to have at least 90% power to detect a HR of 0.70 using a 1-sided log rank test at a significance level of 0.004, and a 2-look group sequential design with Lan-DeMets (O'Brien-Fleming) α -spending function to determine the efficacy boundary.

If either H_{02} or H_{03} are rejected, then OS in patients unselected for PD-L1 expression can be tested at the sum of the significance levels associated with the significant H_{02} and H_{03} tests (see Figure 1). With 534 OS events, the power is 91% (if both H_{02} and H_{03} are rejected), 90% (if H_{02} is rejected and H_{03} is not rejected) or 74% (if H_{02} is not rejected and H_{03} is rejected) to detect a HR of 0.75 using a 1-sided log rank test at a significance level of 0.025, 0.021 or 0.004, respectively, and a 4-look group sequential design with Lan-DeMets (O'Brien-Fleming) α -spending function to determine the efficacy boundary.

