The data cutoff for the primary PFS analysis will occur after the target number of PFS events by BICR assessment in PD-L1 positive patients has been reached and the last patient randomized in the study has been followed for at least 12 months after randomization.

The data cutoff for the primary OS analysis will occur after the target number of deaths in PD-L1 positive patients has been reached.

The study will be considered positive if the stratified log-rank test for either PFS or OS in PD-L1 positive patients is significant at the respective α levels.

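### SAP Tables 7 and 8 run on an earlier calendar than SAP 5.1.2 prescribes, so their look times, the planned IA2/IA3 death counts and the look-by-look stopping probabilities do not describe the written design

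*SAP*

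**What the plan says.** Three timing rules are written down.

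- **Final PFS / IA2.** SAP 5.1.1 and 5.1.2 require 336 BICR PFS events in PD-L1 positive patients and that "the last patient randomized in the study has been followed for at least 12 months after randomization". SAP 2, the protocol summary and protocol 9.1 say the same.
- **IA3.** SAP 5.1.2 and protocol 9.6 place it "15 months after the primary analysis for PFS (IA3 for OS".
- **Accrual.** The sample size assumes "non-uniform patient accrual accomplished over a 21 month period".

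SAP Table 5 (protocol Table 9) plans 195 deaths (53%) at IA2 and 294 (80%) at IA3, out of 368. Its OS efficacy limits from IA2 onwards are "<0.0015 (<-2.9686) <0.0093 (<-2.3524) <0.0180 (<-2.0975". Its IA3 trigger, "15 months after IA2", agrees with the text. Its IA2 trigger is 336 PFS events alone. SAP Table 6 and protocol Table 10, for patients unselected for PD-L1, carry the same triggers with 283 and 427 deaths. The second bullet of protocol 9.6 also leaves out the 12-month condition.

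SAP Tables 7 and 8 are then introduced with the statement that, given the boundaries and "the timing of the interim and final analyses as described above, the design has the following operating characteristics".

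**The concern.** Tables 7 and 8 are where a data monitoring committee or a regulator sees when each look is expected and how likely the trial is to stop there. If they were simulated on another calendar, those statements describe a different trial. The same applies to the 195 and 294 deaths on which the printed IA2, IA3 and final OS limits are built. A later IA3 carries more information, spends more of the OS alpha, and leaves a shorter interval and a lower nominal threshold for the final OS analysis.

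In addition, one analysis has two triggers in controlling text, with and without the 12-month condition, and IA3 is counted from that analysis.

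**Working it through.** **1. Reproducing the plan's figures.** 195/368 = 53.0% and 294/368 = 79.9%. Inputs for the boundaries are a "1-sided log-rank test at a significance level of 0.021" and Lan-DeMets O'Brien-Fleming spending, α(t) = 2[1 − Φ(2.308/√t)], where 2.308 is the upper 0.0105 normal point. At 125/195/294/368 deaths, recursive integration returns z = −3.7913, −2.9686, −2.3524 and −2.0975, all as printed. With drift −ln(0.70)·√368/2 = 3.42, final power is 0.912 without futility stopping, consistent with the claim that "368 OS events for PD-L1 positive patients will be required to have at least 90% power to detect a hazard ratio of 0.70". SAP Table 8 simulates 0.8943 with futility stopping included.

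**2. Calendar, no model needed.** Earliest IA2 = 21 + 12 = month 33. Earliest IA3 = 33 + 15 = month 48.

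| Scenario | Final PFS/IA2 printed | IA3 printed | Gap | Rule |
|---|---|---|---|---|
| HR 1 | 29 | 41 | 12 | at least 33; at least 48; 15 |
| Planned effect (PFS 0.65, OS 0.70) | 32 | 46 | 14 | at least 33; at least 48; 15 |

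Months are printed whole. Rounding lets 32 to 46 stand for 13 to 15 months and leaves month 32 between 0.5 and 1.5 months short of 33. It cannot rescue HR 1: 29 to 41 is 11 to 13 months, and month 29 is at least 3.5 months short.

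**3. Deaths on the written schedule, by interpolating SAP Table 8.**

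- Planned effect, month 33: 195 + (1/14)×99 = 202 (55%). Month 48: 294 + (2/15)×74 = 304 (83%).
- HR 1, month 33: 195 + (4/12)×99 = 228 (62%). Month 48: 294 + (7/12)×74 = 337 (92%).

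**4. Deaths by an event model.** Inputs from the SAP are 580 PD-L1 positive patients randomized 1:1, exponential OS medians of 26.4 and 37.7 months, and 21 months of accrual. The SAP does not give the accrual shape or the drop-out time base, so cumulative accrual (t/21)^k and a constant OS drop-out hazard were fitted to SAP Table 8. The fit is k = 1.70 and 0.00097 per month. It returns 24.5/32.2/46.2/60.9 months against 25/32/46/61 printed (planned effect), and 22.9/29.3/41.0/53.0 against 23/29/41/53 (HR 1). So the printed OS months are where the listed death counts fall under event-driven timing. At months 33 and 48 the model gives 202 (54.8%) and 304 (82.7%) under the planned effect, and 230 (62.4%) and 340 (92.4%) under HR 1. A second calibration (581 patients, accrual density proportional to t^0.6, 5% OS drop-out by month 60) gives 204 and 307, and 233 and 343.

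Applying only the 15-month gap to the printed IA2 months gives IA3 at about 81% (planned effect) or 85–86% (HR 1).

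**5. Effect on boundaries and stopping probabilities** (counts from step 3, no futility stopping).

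| Schedule | Deaths IA2/IA3 | z at IA2/IA3/final | Cumulative P(efficacy) by IA2/IA3/final |
|---|---|---|---|
| Printed counts, HR 0.70 | 195/294 | −2.969/−2.352/−2.098 | 0.317/0.762/0.912 |
| Written rules, HR 0.70 | 202/304 | −2.909/−2.308/−2.106 | 0.355/0.791/0.912 |
| Printed counts, HR 1 | 195/294 | −2.969/−2.352/−2.098 | 0.0015/0.0098/0.0210 |
| Written rules, HR 1 | 228/337 | −2.712/−2.174/−2.138 | 0.0034/0.0159/0.0210 |

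The final nominal p-value limit moves from 0.0180 to 0.0176 (planned effect) or 0.0163 (HR 1). Futility probabilities by look were not recomputed.

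**The case against.** The strongest reply is that nothing in the inference depends on the calendar. The boundaries are functions of event counts. SAP 5.1.2 states them for the planned counts only, and both documents say they will be updated from the events actually observed. That stands. A reader might infer that wrong OS thresholds would be applied or that type I error is at risk. The documents do not support this: the limits are correct at the listed counts. Even if left unchanged at the shifted fractions, they would give a one-sided error of about 0.0207 (planned-effect timing) or 0.0193 (HR 1 timing), both below 0.021.

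A reader might also infer that Tables 5 and 6 contradict the text on IA3. They do not, because both count 15 months from IA2. What those tables lack is the 12-month condition.

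It is fair to add that the larger shift belongs to HR 1. Under the planned effect the shift is about two to three percentage points of information. Across a wide range of accrual and drop-out assumptions (k from 1 to 3, three drop-out settings), planned-effect deaths at months 33 and 48 run from 176 to 224 (48–61%) and from 277 to 324 (75–88%), which includes the printed 53% and 80%. The settings that match SAP Table 8, however, give about 55% and 83%.

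Finally, the 12-month rule does appear in protocol 9.1, so protocol 9.6 can be read as an abbreviated list. But 9.6 is the section that defines the cut-offs, and it should state the full trigger.

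**Conclusion.** The mismatch is established from the documents alone: the calendar columns of SAP Tables 7 and 8 break the 12-month rule and, as printed, the 15-month rule in both scenarios. The exact size of the consequence rests on assumptions, namely exponential survival, calendar time counted from the start of accrual, and the accrual shape and drop-out fitted to SAP Table 8.

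What is wrong is the look times, the planned IA2/IA3 death counts as a description of the written schedule, and the stopping probabilities by look. For example, crossing for efficacy by IA3 under the planned effect is about 0.79 rather than 0.76 on the same calculation. What is not wrong is the set of printed boundaries at their listed counts, the overall type I error, or the final power.

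Two further readings go too far. One is that IA3 practically coincides with final OS. Under HR 1, month 48 is still five months before the printed month 53, though the printed interval is 53 − 41 = 12. Under the planned effect it is 61 − 48 = 13 months against 15 printed. The other is that IA3 should be moved to 294 deaths. A calendar-triggered look with spending-function updating is valid, and the protocol already fixes an IA3 cut-off date of 28 April 2020.

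**What to change.** 1. Re-run and restate SAP Tables 7 and 8 with final PFS at the later of 336 events and month 33, and IA3 15 months after it.
2. In SAP Tables 5 and 6 and protocol Tables 9 and 10, either update the planned IA2/IA3 event counts and the resulting boundaries, or label the present ones as planning values from a purely event-driven schedule.
3. Add the 12-month follow-up condition to the IA2 trigger in protocol 9.6 and in those four tables.
4. State the accrual shape and the drop-out time base used, so that the tables can be reproduced.
5. Keep the 15-month IA3 trigger.

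The cost is one re-run of the design software and a few sentences. No patients, visits or alpha are affected.

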5.2. General Methods

As described in Section 3.4, in this study ‘**treatment arm**’ refers to one of the following:

- Arm A = avelumab plus axitinib;
- Arm B = sunitinib.

Endpoints will be summarized based on the analysis sets described in Table 4 by treatment arm, unless otherwise specified.

5.2.1. Data handling after the cut-off date

Data after the cut-off date may not undergo the cleaning process and will not be displayed in any listings or used for summary statistics, statistical analyses or imputations.

5.2.2. Pooling of centers

In order to provide overall estimates of treatment effects, data will be pooled across centers. The ‘center’ factor will not be considered in statistical models or for subgroup analyses due to the high number of participating centers in contrast to the anticipated small number of patients randomized at each center.

5.2.3. Presentation of continuous and qualitative variables

Continuous variables will be summarized using descriptive statistics i.e., number of non-missing values and number of missing values [i.e., n (missing)], mean, median, standard deviation (SD), minimum, maximum and first and third quartile (Q1 and Q3).

Qualitative variables will be summarized by frequency counts and percentages. Unless otherwise specified, the calculation of proportions will include the missing category.

Therefore counts of missing observations will be included in the denominator and presented as a separate category.

In case the analysis refers only to certain visits, percentages will be based on the number of patients still present in the study at that visit, unless otherwise specified.

5.2.4. Definition of study day

Start day of study treatment is the day of the first dose of study treatment.

The study day for assessments occurring on or after the start of study treatment (e.g., adverse event onset, tumor measurement) will be calculated as:

$$\text{Study day} = \text{Date of the assessment/event} - \text{start of study treatment} + 1.$$

The study day for assessments occurring prior to the first dose of study treatment (e.g., baseline characteristics, medical history) will be negative and calculated as:

$$\text{Study day} = \text{Date of the assessment/event} - \text{start of study treatment}.$$

The study day will be displayed in all relevant data listings.

